### **4.2.3 COPE WP7 Bioresource**

Work Package 7 (WP7) of the COPE project aims to establish a bio-repository with biological specimens from clinical trials to support research work relevant to improving the outcomes of kidney and liver transplantation. Using the bio-repository, WP7 aims to identify bio-markers that can be used to predict the outcomes of transplantation. These include markers detected during and after machine preservation and as a consequence of ischemia reperfusion injury. Sample types include blood, perfusate and tissue specimens. Next generation high throughput -omics technology, including proteomics and metabolomics, will be used to evaluate and short-list candidate biomarkers that will be used in conjunction with clinical trial

data. WP7 will support further sub-studies and promote collaborations, through establishing an access policy for samples to be used in research projects outside of the funding scope of the FP7 grant.

The nature and timing of samples to be collected for this bioresource as part of the present study are detailed in appendix A.

### **4.3 TRIAL PARTICIPANTS**

#### **4.3.1 Overall description of trial participants**

All ECD kidneys allocated to one of the participating study centres and complying with the inclusion criteria for participant and donor organ selection will be included in the study. Organ allocation and logistics will be unchanged by the study. Logistics will follow standard policies of the participating centres and the study should not change any procedure or the timing of transplantation in individual recipient centres. The participants in the study are all patients registered with EuroTransplant or NHSBT on the kidney transplant waiting list. Donor organs are allocated according to standard procedures.

#### **4.3.2 Inclusion criteria donor kidneys**

All kidneys from DBDs fulfilling the UNOS-ECD criteria; donors >60 years old, or >50 yrs with 2 of the following; hypertension, terminal creatinine >1.5mg/dL or cerebrovascular cause of death.

#### **4.3.3 Inclusion criteria transplant participant**

- Participant is 18 years old or older.
- Listed for renal transplantation due to end stage renal disease on the ET or NHSBT renal waiting list within one of the participating centers.
- Participant is willing to participate in the study and has provided written informed consent.
- This transplantation is the participant's first or re-transplantation.

#### **4.3.4 Exclusion criteria donor kidney**

- Kidneys used for a multi-organ transplant procedure (like Kidney-Pancreas, Kidney-Liver, etc.)
- Kidneys from standard criteria donors (SCD).

- Kidneys procured from DCD donors (i.e. donation after cardiac death) Kidneys used for a double kidney transplant within the same recipient.
- Kidneys procured from donors older than 85 years

Kidneys with multiple renal arteries or missing aortic patch should NOT automatically be excluded from the study. The group allocation should NOT be switched if one of the kidneys demonstrates a more challenging arterial anatomy than the other.

#### **4.3.5 Exclusion criteria transplant participant**

- Simultaneous participation in another perfusion trial
- Scheduled to undergo multi-organ transplantation
- Planned dual-kidney transplantation
- Is unable or unwilling to provide informed consent

#### **4.3.6 Exclusion after randomisation**

If a kidney is judged not transplantable after randomization this case will be documented with reasons for exclusion and will be excluded from the study.

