## 4 TRIAL DESIGN

### 4.1 SUMMARY OF TRIAL DESIGN

The study will be conducted as a prospective, randomized, parallel group, single blinded, controlled, multi-centre, non-paired superiority trial; allocation will be on a 1:1 basis and an intention-to-treat method will be used to analyze the results.

After accepting the potential ECD organ for donation, kidneys will be allocated following the standard Eurotransplant/ UK-transplant allocation rules.

In a non-paired-design, each ECD kidney that has been accepted for transplantation by one of the participating centres will be randomly assigned to SCS or to SCS followed by reconditioning by end-ischemic oxygenated HMP (HRMP+O2). Randomizing kidneys after they have been accepted for transplantation avoids a potential bias that acceptance of the kidney is being influenced by the preservation modality.

[figure not shown]

If two kidneys are accepted for transplantation by the same centre the surgeon will decide which kidney to transplant first according to their local protocol.

It is not essential for both kidneys from a donor to enter the trial. If only one of the kidneys is deemed transplantable, it can still be included in the trial analysis.

Exceptionally anatomical situations may not allow connection of a kidney to the perfusion circuit. In this situation the kidney should be preserved by cold storage alone even though it was randomized to HRMP+O2.

Anticipated flow of patients through the trial is depicted below

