#### **4.4.4.4 Blinding**

Transplant participants will be blinded.

Care providers will not be blinded for the treatment arm.

Routine laboratory parameters will be analysed in the central university laboratory not knowing about the allocation to the study groups

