In order to allow marginal kidneys to be connected to the perfusion pump as long as possible after arrival at the transplant center, kidneys will be completely prepared for transplantation prior to being placed on the device, if possible. This will allow keeping the kidney on the pump until the recipient vasculature has been completely prepared for implantation of the organ. If applicable, cross-match testing will be performed during machine perfusion time, which is expected to allow a minimum perfusion time of at least 2 hours. In case of a positive cross match or a medical reason due to which the patient cannot undergo transplantation, the kidney will be re-allocated. The accepting transplant center will be able to choose whether they would like the kidney to be transported while connected to the perfusion machine or prefer the kidney to be disconnected from machine perfusion, in which case, the kidney will be placed in cold storage solution.

Use of machine preservation should not prolong the total ischemia time. Total perfusion time as well as total cold ischemia time (CIT) will be recorded.

Perfusion measurements will not be used for accepting/ discarding kidneys. In order to verify whether the kidney is being adequately perfused, the study coordinator will record perfusion flow and renal resistance (RR) at 15 minutes after initiation of perfusion. Any necessary corrective actions will be recorded (check for leakages, obstructions, re-cannulation, etc). Also at the end of perfusion, final flow, RR and temperature will be recorded by the study coordinator. All machine perfusion data will be downloaded at the end of each case. Perfusion parameters such as flow and renal vascular resistance will be hidden to the transplant team. The study coordinator will not be directly involved with recipient care.

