## **6 STATISTICS**

### **6.1 DESCRIPTION OF STATISTICAL METHODS**

The primary analysis of the trial will be an intention-to-treat analysis comparing intervention (HRMP) against control (SCS) for all primary and secondary outcomes. The primary endpoint, one year graft survival, will be analysed using logistic regression with adjustment for stratification factors. Additional analyses adjusting for other important prognostic factors will also be undertaken. Binary outcomes will be assessed using chi-squared tests and logistic regression to adjust for prognostic factors. Continuous outcomes will be compared using the T-test if normally distributed, otherwise using the Mann-Whitney U test. Time-to-event outcomes will be analysed using survival analysis methods, including Kaplan-Meier plots and Cox proportional hazards regression model with calculation of hazard ratios. Outcomes will be reported with 95% confidence intervals and two-sided p-values to 3 decimal places.

A secondary analysis of the primary endpoint will be done as per protocol.

A Statistical Analysis Plan (SAP) containing a detailed description of the statistical methods will be drafted as a separate document early in the trial and finalised prior to the final data lock.

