## **6.2 NUMBER OF PARTICIPANTS**

### Sample size calculation

Based on the previously published paper by Treckmann et al., the 1-year graft survival for ECD kidneys preserved by SCS is being estimated at 80%. The use of HRMP is being hypothesized to improve 1-year graft survival from 80% to 92% based upon the improvement in graft survival of ECD kidneys seen in the MP Trial.

For a power of 80% with Type I error (alpha) of 5%, in a two-sided statistical model, the required sample size to detect an improvement in 1-year graft survival from 80% to 92% is 131 kidneys in each treatment arm, 262 in total.

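### Section 4.3.6 removes randomised kidneys later judged not transplantable, which conflicts with the intention-to-treat primary analysis and leaves a possible device effect out of the arm comparison

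*Protocol*

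**What the plan says.** Protocol section 4.4.4.1 randomises individual kidneys 1:1. Section 4.1 places randomisation after acceptance of the organ and gives the reason: "Randomizing kidneys after they have been accepted for transplantation avoids a potential bias" in which the preservation method influences acceptance. Sections 4.1 and 6.1 both commit to intention-to-treat, and 6.1 applies it to all primary and secondary outcomes.

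Section 4.3.6 then says: "If a kidney is judged not transplantable after randomization this case will be documented with reasons for exclusion and will be excluded" from the study.

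Other passages bear on this rule:

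- **4.4.4.4 Blinding:** "Care providers will not be blinded for the treatment arm".
- **4.4.4.5 Emergency unblinding:** discarding a kidney is an example of a complication that the preservation method might bring about.
- **4.5.1 Machine perfusion study group:** perfusion measurements may not drive the decision to accept or discard, and flow and resistance are concealed from the transplant team. After a positive cross-match, or where "the patient cannot undergo transplantation, the kidney will be re-allocated", nothing is said about the kidney's later status in the trial.
- **6.7 Inclusion in analysis:** kidneys that cannot be connected to the device stay in the perfusion arm. The choice of analysis populations is otherwise left to the SAP.
- **4.2.1 Primary outcome measures:** graft survival is counted at 12 months from transplantation.

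**The concern.** Randomising after acceptance protects the comparison only if the acceptance decision is not reopened once the arm is known. Section 4.3.6 reopens it, and the decision falls to people who know the allocation. Perfused kidneys also receive extra handling, including cannulation of the renal artery (Appendix E), which could reveal or cause damage. A discard can therefore be a consequence of allocation.

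If doubtful kidneys are removed more often from one arm, that arm's 1-year graft survival improves with no benefit to anyone. A kidney lost because of the device never counts against it. The exclusion is from the study, not from one analysis, so a SAP that restored these kidneys would contradict the protocol. The protocol is also inconsistent with itself: section 6.7 keeps one kind of post-randomisation problem in the assigned arm, and section 4.3.6 removes another.

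**Working it through.** **Inputs.** From section 6.2: 1-year graft survival 80% (control) vs 92% (perfusion), two-sided alpha 5%, power 80%, and a required size that "is 131 kidneys in each treatment arm, 262 in total". Discard counts are assumptions, because the protocol gives no rate.

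**Step 1. Reproduce the plan's figure.** Pooled-variance formula, mean survival 0.86:

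n = [1.96·√(2·0.86·0.14) + 0.842·√(0.80·0.20 + 0.92·0.08)]² / 0.12² = 1.873 / 0.0144 = 130.1, rounded up to 131 per arm.

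Power at 131 per arm is 80.3%. The sample size is reproduced and is not at fault.

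**Step 2. Count discards as failures.** Randomise 131 per arm, let d kidneys be discarded, and let a fraction f of the transplanted kidneys fail (0.20 control, 0.08 perfusion). Failure among all randomised kidneys is

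F = [f·(131 − d) + d] / 131.

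Example with d = 2 (control) and d = 4 (perfusion): (0.20·129 + 2)/131 = 27.8/131 = 21.2%, and (0.08·127 + 4)/131 = 14.16/131 = 10.8%.

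The test is z = D / √(2·p̄·(1 − p̄)/131), where D is the difference in F and p̄ the mean of the two F values.

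| Discards, control vs perfusion | F control | F perfusion | Difference | p |
|---|---|---|---|---|
| 0 vs 0 | 20.0% | 8.0% | 12.0 points | 0.005 |
| 2 vs 4 | 21.2% | 10.8% | 10.4 points | 0.02 |
| 2 vs 6 | 21.2% | 12.2% | 9.0 points | 0.051 |
| 1 vs 7 | 20.6% | 12.9% | 7.7 points | 0.095 |
| 4 vs 4 | 22.4% | 10.8% | 11.6 points | 0.01 |
| 6 vs 6 | 23.7% | 12.2% | 11.4 points | 0.016 |

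The smallest significant difference must be taken at each scenario's own pooled rate. At the planning rate it is 1.96·√(2·0.86·0.14/131) = 8.4 points. In the three unbalanced rows pooled failure is about 16% to 17%, and the threshold is about 8.9 to 9.0 points. That is why 2 vs 6 falls just short.

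**Step 3. The reverse error.** Suppose there is no true effect (80% of randomised kidneys survive in both arms), and k perfused kidneys that would have failed are excluded. Apparent survival in the perfusion arm is 0.80·131/(131 − k):

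- k = 4: 104.8/127 = 82.5%; chance of p < 0.05 about 8%.
- k = 7: 104.8/124 = 84.5%; about 16%.
- k = 13: 104.8/118 = 88.8%; about 48%.

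The nominal figure is 5%. This is a worst case, because every excluded kidney is assumed to be one that would have failed, and all come from one arm.

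**Step 4. The benign case.** If 5% of kidneys are lost equally from both arms, unrelated to outcome and not replaced, about 124 per arm remain and power is 78%.

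**The case against.** The strongest reply is that the primary endpoint starts at transplantation, so it is undefined for a kidney that is never transplanted. A transplanted-kidney population is then a recognisable modified intention-to-treat set, and the fault is mainly one of labelling. Counting discards as failures creates a different, composite endpoint and also counts defects that were present before allocation. This stands to the extent that the all-randomised analysis belongs beside the main analysis as a sensitivity analysis. It does not rescue section 4.3.6, which removes the kidney from the study while 6.1 claims intention-to-treat without qualification.

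Safeguards are also real. Perfusion readings are concealed and may not drive discard, allocation is hidden until the patient is recruited and baseline data are recorded (4.4.4.2), and unconnectable kidneys stay in their arm. These narrow the route to bias. They do not conceal the arm, the kidney's appearance or damage from cannulation.

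Two stronger readings are tempting, and the protocol does not support either.

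- **Re-allocated kidneys also leave the trial.** Section 4.5.1 says only that they are re-allocated. Departure is an inference, for instance if the new recipient is not in the trial. A positive cross-match also has no evident link to the arm.
- **The rule hides a device effect.** Section 4.3.6 requires each case and its reasons to be documented, and sections 5.7 and 5.14 cover the reporting of device deficiencies even without an adverse event. What is missing is the place of these kidneys in the arm comparison.

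Finally, section 6.7 leaves analysis populations to the SAP, which was not available here. That would answer an omission. It does not answer a rule that the protocol has already fixed.

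**Conclusion.** The point holds for section 4.3.6. As written, the rule contradicts the intention-to-treat commitment in 4.1 and 6.1, is out of line with 6.7, and can bias the primary comparison through an event that the protocol itself links to preservation.

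The size depends on imbalance. An excess of two perfused discards leaves the planned result significant, an excess of four makes it borderline, and an excess of six loses it. Balanced discards change little. These figures assume the planned 20% vs 8% failure among transplanted kidneys, 131 randomised per arm, and a normal-approximation test in place of the adjusted logistic regression of 6.1. Nothing in the protocol shows that an imbalance will occur. But with these kidneys out of the study, the planned comparison cannot show whether one did or what it changed.

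For re-allocated kidneys the finding is limited to an unstated study status.

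**What to change.** 1. Reword 4.3.6 so that every randomised kidney stays in the trial dataset in its assigned arm, with the reason recorded if it is not transplanted.
2. Reconcile 4.1, 6.1 and 6.7 with this, and call the analysis of transplanted kidneys modified intention-to-treat.
3. Pre-specify a sensitivity analysis of the primary endpoint in all randomised kidneys, counting discards as failures in the assigned arm.
4. Report discards by arm with reasons.
5. State that re-allocated kidneys are analysed in their assigned arm where data and consent allow, and report their number by arm.
6. State in 6.3 whether kidneys that are not transplanted count towards the 262.

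The cost is protocol wording and one further analysis, on discards that are already to be documented. Its estimate may be slightly less favourable. It also has less power if discards fall mainly on the perfusion arm: with four such discards and none in controls, survival is 0.92·127/131 = 89.2% against 80%, and power is about 54%. It should therefore be read as a check on the main result.

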### **4.4 STUDY PROCEDURES**

#### **4.4.1 Informed consent**

The emergency nature of kidney transplantation means that once a potential participant is called in for a transplant there will be a 3-4 hour window for the consent and screening process to occur. This does not allow sufficient time for the potential participant to consider the full implications of participating in the study. For this reason, we will ask the potential participants at the moment of availability of the donor organ only the essential informed consent for that given moment (i.e. biopsy, drawing of blood during transplantation and a questionnaire). After transplantation the participant will receive further information and will be given a week to consider complete informed consent for use of clinical data on follow-up and the two remaining questionnaires.

At that moment we will inform them that we would want to take their consent for access to their data. Patients will have the opportunity to discuss this with a trained individual involved in the trial if they would like via a telephone number that will be included in the patient information letter, handed to them at the moment of arrival in the hospital.

If the patient is not willing to participate in the study then the kidney preservation will be carried out using conventional procedures. If the patient is willing to consent for access to their data, but not for extra biological samples to be taken, they will not be excluded from the study. If the patient is not willing to allow access to their data they will be excluded from the study and biological samples will be destroyed. Since the biopsy is taken routinely, it will not be destroyed, but only be used for the routine, clinical purposes.

The participant will also be required to complete a surgical consent form for the transplant procedure as per standard local policy.

The participant must personally sign and date the latest approved version of the informed consent form before any study specific procedures are performed. Written and verbal versions of the participant information sheet and informed consent form will be presented to the participants detailing the exact nature of the study, the implications and constraints of the protocol, the known side effects and any risks involved in taking part. It will be clearly stated that the participant is free to withdraw from the study at any time for any reason without prejudice to future care, and with no obligation to give the reason for withdrawal. The participant will be allowed as much time as possible to consider the information, and the opportunity to question the investigator, or other members of the clinical or research team, to decide whether to participate in the study.

A copy of the signed Patient Information Leaflet, as well as the signed and dated consent form will be given to the participant. The original signed form will be retained at the study site and a copy will be placed in the medical notes.

Subjects are free to withdraw consent at any time, irrespective of their initial consent. Subjects who withdraw consent will be replaced.

Each subject must also give permission for the sponsor's representatives to review their hospital records for the purpose of source document verification.

The subject's general practitioner/family doctor will be informed of their participation in the study.

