##### **4.4.4.2 Allocation: Concealment mechanism**

Allocation concealment will be ensured by use of central computerised randomisation (with telephone backup). Allocation will not be revealed until the patient has been recruited to the trial and donor and recipient baseline characteristics have been recorded. Random permuted block length will be used; block sizes will not be disclosed

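### Consent to use follow-up data is sought after randomisation and transplantation and refusers are excluded, so the set called intention-to-treat is selected after allocation

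*Protocol*

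**What the plan says.** Consent has two stages in section 4.4.1. Before transplantation the patient agrees only to a biopsy, blood sampling during the operation and one questionnaire. After transplantation the patient receives further information and "will be given a week to consider complete informed consent for use of clinical data on follow-up". On refusal the rule is: "If the patient is not willing to allow access to their data they will be excluded from the study". The same section adds: "Subjects who withdraw consent will be replaced". Section 4.8 names withdrawal of consent to data access, or loss to follow-up, as the only withdrawals expected. This suggests that the replacement sentence is meant to reach patients who refuse data access.

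Randomisation comes earlier. Section 4.1 assigns each kidney once it has been accepted for transplantation, and under 4.4.4.2: "Allocation will not be revealed until the patient has been recruited to the trial". Sections 4.1 and 6.1 both call the analysis intention-to-treat. Section 6.7 leaves the detailed selection of participants to the SAP.

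**The concern.** An intention-to-treat comparison is protected because membership is fixed at randomisation. Here a patient's membership depends on a decision made after allocation, while the first evidence on the graft is coming in. A patient on dialysis or with an early graft loss may be less willing to allow further use of data than a patient whose kidney works. Early graft function is also what the intervention is meant to improve. If such patients drop out equally in both arms, the observed effect shrinks. If they drop out unequally, a difference can appear where none exists. Recruiting replacements restores the count, not the comparison.

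The SAP cannot fully repair this. It can define and name the analysis set, but it cannot bring back data that the trial may not access.

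**Working it through.** **Order of events in the protocol**

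1. The kidney is accepted and randomised (4.1). Allocation is released once the patient is recruited and baseline data are recorded (4.4.4.2).
2. The first, limited consent is given before transplantation (4.4.1).
3. On days 1 to 7, creatinine, dialysis, graft survival and recipient survival are recorded daily (Appendix B). Delayed and slow graft function are defined over the first 7 days, and graft survival is read at day 7 (4.2.2).
4. Consent to use follow-up data is sought after transplantation, with a week to decide. Refusal means exclusion (4.4.1).

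Steps 3 and 4 overlap, and both follow step 1.

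**The plan's own figure.** Section 6.2 gives 80% vs 92% survival, two-sided alpha 5% and power 80%. With mean survival 0.86:

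n = [1.960·√(2·0.86·0.14) + 0.842·√(0.80·0.20 + 0.92·0.08)]² / 0.12² = [1.960·0.4907 + 0.842·0.4833]² / 0.0144 = 130.1, rounded up to 131 per arm. This matches the protocol, and power at 131 is 80.3%.

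**Loss equal in both arms.** All loss rates below are assumptions, because the protocol gives none.

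*Model A: only early failures are lost.* Let f be the 12-month failure rate (20% vs 8%), w the share of failures that fall in week 1, and x the share of those lost. Observed failure = (f − f·w·x) / (1 − f·w·x). Power is for the numbers retained.

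| w | x | Observed failure | Difference (points) | Power |
|---|---|---|---|---|
| 25% | 10% | 19.6% vs 7.8% | 11.8 | 79.4% |
| 50% | 10% | 19.2% vs 7.6% | 11.6 | 78.5% |
| 50% | 25% | 17.9% vs 7.1% | 10.9 | 75.5% |
| 50% | 50% | 15.8% vs 6.1% | 9.7 | 69.5% |

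Topping the last row back up to 131 per arm gives 70.9%.

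*Model B: 5% of all other patients also refuse.* Let S be survival, e early loss and L = 1 − S − e late loss. Refusal after early loss is r, and 131 per arm are analysed. Observed survival = 0.95·S / [0.95·S + 0.95·L + (1 − r)·e].

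- Mildest case (e = 5% control, 2% intervention; r = 30%): 81.1% vs 92.5%, an 11.4-point difference, power 78.2%.
- Most severe case (e = 10% control, 3.2% intervention; r = 50%): control 0.760 / (0.760 + 0.095 + 0.050) = 84.0%; intervention 0.874 / (0.874 + 0.0456 + 0.016) = 93.4%. The difference is 9.4 points and power about 68%.

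With equal loss and no true effect, both arms shift alike and type I error stays at 5%.

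**Loss that differs by arm, no true effect (80% survival in both), 131 analysed per arm**

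| Assumption | Spurious difference (points) | Type I error |
|---|---|---|
| Model A, w = 50%, x = 10% vs 20% | 0.8 | 5.3% |
| Model B, e = 5%, r = 5% vs 30% | 1.1 | 5.5% |
| Model B, e = 10%, r = 5% vs 30% | 2.2 | 7.3% |
| Model A, w = 50%, x = 20% vs 60% | 3.5 | 11.7% |
| Model B, e = 10%, r = 5% vs 50% | 4.0 | 13.3% |

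The sign depends on which arm loses more early failures.

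**The case against.** The strongest reply is that the size is unknown and may be trivial. Few patients may refuse, and the patient who decides is blinded (4.4.4.4), so refusal driven by knowledge of the arm is unlikely. Refused data cannot be analysed in any trial, and 6.7 leaves analysis sets to the SAP. Staged consent also has an ethical reason, since 4.4.1 argues that the 3 to 4 hours before surgery are too short for full consideration. All of this stands and lowers the severity. It does not remove refusal that follows early graft function, nor the mismatch with the intention-to-treat label.

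A reader might also infer stronger points that the protocol does not support:

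- **Everyone who does not sign is excluded, including those who die.** Section 4.4.1 excludes patients who are unwilling. For death or incapacity before the second consent, no rule is stated. Section 4.8 lets relatives or a proxy withdraw consent for an included patient who loses capacity, without saying which consent is meant. The defect is a gap, not a stated exclusion.
- **Staff who know the allocation take the second consent.** Care providers are unblinded, but no section says who seeks this consent.
- **The scheme contradicts 4.4.4.2.** A decision to participate precedes the intervention, so recruitment at the first consent followed by release of allocation is consistent.
- **Primary non-function is already known.** It is defined at 3 months (4.2.2). Only delayed and slow function and early graft status are visible in the first week, and delayed function need not end in graft loss.
- **Replacement itself creates the bias.** It adds patients and removes none. The exclusion is the problem. The replacement sentence speaks of withdrawal, so its reach to refusers rests on 4.8.

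**Conclusion.** The concern holds as a structural inconsistency. The protocol lets exclusion occur after allocation, and possibly in relation to early outcome, in a set that it calls intention-to-treat. It should be fixed, but no large bias has been shown.

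The ranges rest wholly on assumed early-loss and refusal rates. Equal outcome-related loss turns a true 12-point difference into about 9.4 to 11.8 points, with power about 68% to 79% and no effect on type I error. Loss differing by arm gives a spurious difference of about 1 to 4 points and type I error of about 5% to 13%. Participant blinding makes the equal-loss pattern the more likely of the two. With few refusals either effect is negligible.

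**What to change.** 1. In 4.4.1, state that outcome data are excluded only on active refusal. With ethics approval, state that patients who die or lose capacity before the second consent stay in the trial with a minimal dataset of graft and patient status.
2. Delete "Subjects who withdraw consent will be replaced", or state that additional recruits do not substitute for randomised participants. Keep data up to withdrawal where permitted.
3. If refusers' data cannot be used, call the primary set modified intention-to-treat. Report refusals by arm and by day-7 graft status, and add a best-case/worst-case sensitivity analysis of the primary endpoint.
4. Subject to ethics approval, add consent to the minimal outcome dataset to the form signed before randomisation, and use the later week for reconfirmation or opt-out.

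Items 1 and 2 are mainly wording, and item 3 is analysis and reporting; none needs extra patients or procedures. The cost is a protocol and consent amendment with ethics review for the participating centres. Item 4 costs most: it adds an item to a short consent discussion and partly reverses the protocol's reason for staging consent. The first three are therefore worth making even if it is refused.
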